- 3) Provide the plan for data analysis (include as applicable the sample size calculation)

Please respond to all components of this item, or clearly indicate which components are not applicable.

STUDY TIMELINE:

Form A

IRB Velos	STU-2018-0192 26783
--------------	------------------------

month	Year 1			Year 2			Year 3			Year 4			Year 5		
	1-3	4-11	12	1-5	6	7-11	12	1-5	6	7-11	12	1-5	6	7-11	12
Set-up, hiring															
Recruitment															
Testing															
Project Meeting															
Data Analysis															
Conferences															
Manuscripts															

PROCEDURES INVOLVED:

The sequence of experiments is shown in Fig. 1. During month one, all eumenorrheic subjects (nOCs), will provide blood samples every other day to track their hormones across the menstrual cycle (they will track menstrual cycle for 2-3 months prior). Post hoc analyses will compute subject-specific hormonal fluctuations throughout the month using a nonlinear mixed-effect model. nOCs will use urinary ovulation kits to verify that they have ovulatory cycles and identify the approximate day of ovulation. nOCs and male controls will have a brain MRI to establish consistent coil placement across visits in Aim 3, where TMS will be used to assess cortical excitability.

In month 2, all female subjects, both OCs and nOCs, will undergo every other day testing as described in Aims 1 and 2 (described in detail below) and provide every other day blood samples. nOC subjects will use urinary ovulation kits daily as described above. Hormone concentrations of each nOC subject will be compared to the subject-specific mixed-effect model from month one to determine where she is in her menstrual cycle. This estimation will enable TMS testing at six key points during the cycle (Aim 3). For example, when the subject's daily estradiol concentrations are rising and the model indicates that her peak estradiol should occur the next day, she will be instructed to report to the lab for TMS testing in the next 24 hours. On these days, she will complete the protocols for Aims 1-3. Subjects will be randomized to start testing in the follicular, peri-ovulatory, or luteal phase where Day 1 is defined as the first day of menses.

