The time required for each experiment, including setup, is approximately 2½ to 3 hours for Aims 1 and 2 combined and 2 - 3 hours for Aim 3. The investigator will be blinded to menstrual cycle phase and contraceptive use. The comparative groups for Aims 1 and 2 will be women on monophasic oral contraceptives containing progestins of similar potency and androgenicity, as justified by our published and pilot data. The control group for all Aims will be age-matched healthy males. Our choice of males as

[figure not shown]

Figure 1. Sequence of experiments. In month one, non-users of oral contraceptives will have their blood drawn to determine their hormonal signature. In month two, subjects will undergo daily blood draws as well as testing for Aims 1 and 2. Subjects will complete tests for Aim 3 on six occasions defined by key hormonal fluctuations.

Form A

IRB Velos	STU-2018-0192 26783
--------------	------------------------

controls for Aim 3 is motivated by the lack of data to guide interpretation of the effects of exogenous hormones on cortical circuitry.

Below is the specific experimental protocol for each AIM:

AIM 1: Determine the influence of sex hormone fluctuations on muscle stretch reflex at relaxed and active states.

Venipuncture will be performed at UT Southwestern Medical Center or UT Southwestern Lab. Venipuncture will be completed every other day during a full menstrual cycle, for a total of 2 cycles. This equates to 28 to 40 blood draws total (not necessarily consecutively), up to 3.04 teaspoons of blood per draw, for a maximum of 85.12 to 121.6 teaspoons (425.6 ml to 608 ml) over the course of study participation (2 – 3 months, equivalent to 2 menstrual cycles). To minimize the effect of diurnal fluctuations of hormone levels, testing will be done at a consistent time of day for each test session across all Aims. Furthermore, OCs will be asked to ingest their birth control pill at a consistent time each every day of the testing.

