All necessary data pertaining to the study from SRAlab will be transferred to UT Southwestern Medical Center. Data (except for blood samples) will be maintained for future use, for indefinite amount of time. All data would be de-identified and stored in a protected database. Researchers only with IRB approval and approval from authorized personnel of this study, would have access to the controlled database of data, to be used to answer questions related specifically to their research study.

SAMPLE SIZE JUSTIFICATION

AIMS 1 and 2: We wish to rule out an effect of hormonal state on motor neuronal excitability. To do this, specified the minimum effect size that we considered meaningful along with high statistical power that minimized the chances of a Type-I error. We conducted statistical simulations to evaluate this scenario. Pooling $N = 30$ OCs and $N = 30$ nOCs that provide daily H-reflexes from soleus muscle (Aim 1) and MSR from 3 quadriceps muscles (VM, VL, RF) over one menstrual cycle provided power = .95 to detect effects as small as an average within-individual correlation of $r = -0.075$ ($R^2 = .005$) between a single hormone and reflex responses across a range of situations. Smaller differences are considered as pragmatically meaningless. This degree of power holds even if menstrual cycles vary from 22 to 32 days, and participants miss an average of 25% (see above) of their lab visits (and assumes the data are missing at random).

AIM 3: To test hypothesis 3, that estradiol will produce a targeted facilitatory influence on lower limb muscles, we used a GEE model that views the mean conditioned MEPs at each ISI as correlated outcomes before separate post-hoc tests for each inter-pulse interval (ISI = 7, 10, 15, 20, 25, 30 ms) and each subject between peak estradiol and baseline hormone concentration (Fig. 7). This synthesis establishes a within-

Form A

IRB Velos	STU-2018-0192 26783
--------------	------------------------

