Likely These risks are expected to occur in more than 20 out of 100 subjects.	•	•
Less likely These risks are expected to occur in 5-20 subjects or less out of 100 subjects.	•	•
Rare These risks are expected to occur in less than 5 subjects out of 100		•

Form A

IRB Velos	STU-2018-0192 26783
----------------------------	--------------------------------------

		
4.d. List ALL other research procedures or components not listed in table 4.b. The combination of Tables 4b and 4d should account for all of the research procedures that will take place during this study.
 
Consider grouping similar procedures under a single component (e.g., blood work, CT = safety assessments)
			
#		Research component	Column A	Column B	
		
 individual procedures 
example: Eligibility Assessments 
 History and physical Questionnaire Laboratory tests 
 
Add or delete rows as needed
	Local Standard Practice Indicate the number of times each procedure will be performed as stipulated in the research plan that would be performed if the participant were not participating in the study.	Research Only Indicate the number of times each procedure will be performed solely for research purposes (meaning that the participant would not undergo the same number of procedures or would not undergo the procedure(s) at the same frequency if they were not participating in the study)	Column D Risks If you are requesting a Waiver of Informed Consent, complete the table below. List the reasonably expected risks for each procedure or group of procedures under the following categories as appropriate: 
 • Serious and likely; • Serious and less likely; • Serious and rare; • Not serious and likely; • Not serious and less likely
1	Aim 1	N/A	Every other day, for a menstrual cycle	N/A	
	Blood draw for Estradiol, Progesterone, and Testosterone				
	Reflex testing				
	Anterior Knee Laxity Measurement				
2	Aim 2	N/A	Every other day, for a menstrual cycle	N/A	
	Blood draw for Estradiol, Progesterone, and Testosterone				
	EMG/Nerve conduction Testing				
3	Aim 3	N/A	5 – 6 times in a menstrual cycle	N/A	
	TMS	N/A	once	N/A	
	MRI	N/A	5 – 6 times	N/A	
4	Aim 4	N/A	Every day for a menstrual cycle, until ovulation	N/A	
	Blood analysis on microRNA,	N/A	2	N/A	
	Blood analysis for DNA sequencing	N/A	2	N/A	
	Blood analysis on mRNA	N/A	2	N/A	
5	Ovulation testing	Urine Ovulation Kit	1.		

Form A

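### The .95 power for Aims 1 and 2 is stated for daily reflex testing, but testing is scheduled every other day, so it is not supported for the planned schedule

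*Combined protocol and SAP*

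**What the plan says.** Section 4.a, Sample Size Justification, Aims 1 and 2, reports a simulation. The population is 30 oral contraceptive users pooled with 30 "nOCs that provide daily H-reflexes from soleus muscle (Aim 1) and MSR from 3 quadriceps muscles (VM, VL, RF) over one menstrual cycle". The claimed power is .95 for an average within-individual correlation of -0.075 between one hormone and the reflex response. It is said to hold for cycles of 22 to 32 days and an average of 25% missed visits. The declared purpose is to rule out a hormonal effect, and smaller correlations are treated as of no practical importance.

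The schedule reads differently:

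- Section 4.a, Procedures Involved: "In month 2, all female subjects, both OCs and nOCs, will undergo every other day testing as described in Aims 1 and 2", "and provide every other day blood samples".
- Section 4.d, procedures table, rows for Aims 1 and 2: "Every other day, for a menstrual cycle".
- Section 4.a, Aim 1: "Venipuncture will be completed every other day during a full menstrual cycle, for a total of 2 cycles". The count follows: "This equates to 28 to 40 blood draws total".

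Some text points the other way. The Figure 1 legend describes the month-two blood draws as daily, and the TMS timing example refers to a point when "daily estradiol concentrations are rising and the model indicates that her peak estradiol should occur the next day". For TMS days the plan adds: "On these days, she will complete the protocols for Aims 1-3". Non-users may therefore have some reflex sessions beyond the alternate-day ones.

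**The concern.** The power is stated for about twice as many sessions as the schedule provides, and nowhere is it restated for every-other-day testing. Either the word daily is left over from an earlier design while the simulation used the current schedule, or the simulation itself used daily sessions. The documents do not say which.

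This matters because Aims 1 and 2 are framed around excluding an effect. The .95 at -0.075 is the only support offered for reading a null result as absence of a meaningful effect. If the correlation detectable with .95 power is nearer .10, a null result would leave open effects that the plan itself calls meaningful.

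**Working it through.** **Inputs.** From the sample size section: 60 women, r = -0.075, power .95, cycles of 22 to 32 days (midpoint 27), 25% missed. From Procedures Involved and the 4.d table: testing every second day. Alpha for Aims 1 and 2 is not stated; I assume two-sided 5%.

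**Can .95 be reproduced?** Not uniquely, because the model, the between-muscle correlation and the serial correlation are not given. It is attainable for daily testing. Use power = Φ(atanh(.075) × √n − 1.960) with n = 60 × sessions × k / (1 + (k − 1)ρ). Three muscles (k = 3), an assumed ρ = .3 and 27 × .75 = 20.25 sessions give n = 2,278 and power .948. The same inputs with 10.125 sessions give n = 1,139 and power .718.

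**Session counts (no alpha or correlation needed).**

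| Case | Sessions |
|---|---|
| Daily, 27 days, 25% missed | 60 × 27 × .75 = 1,215 |
| Daily, 22 days, 25% missed (thinnest case claimed) | 60 × 22 × .75 = 990 |
| Every other day, 27 days, 25% missed | 60 × 13.5 × .75 = 607.5 |
| Every other day, 27 days, none missed | 60 × 13.5 = 810 |
| Every other day, 32 days, none missed | 60 × 16 = 960 |

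The share of daily sessions absent under the schedule with 25% missed is 1 − .5 × .75 = .625 at any cycle length. Before any extra TMS-day sessions, even full attendance over a 32-day cycle stays below 990.

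**Illustrated power.** Take .95 as right for daily testing, so the noncentrality is 1.960 + 1.645 = 3.605. Then power = Φ(3.605 × √ratio − 1.960), and the r detectable at .95 is .075/√ratio, where ratio is the information kept. Days are treated as independent.

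- *.95 exact at 27 days:* ratio 607.5/1,215 = .500, power .722, r .106. Losing one degree of freedom per woman, (10.125 − 1)/(20.25 − 1) = .474, power .699, r .109.
- *.95 a floor reached at 22 days:* ratio 607.5/990 = .614, power .806, r .096. With the degree of freedom, (10.125 − 1)/(16.5 − 1) = .589, power .790, r .098.

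**Factors that shrink the loss (floor reading).**

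- *Extra TMS-day sessions for the 30 non-users, 25% missed (3 or 6 each, assumed):* 675/990 = .682, power .845; 742.5/990 = .750, power .877.
- *Between-woman slope variance as a share s of total (assumed), ratio 1/(s + (1 − s) × 990/607.5):* s = .5 gives .761, power .882; s = .9 gives .941, power .938.
- *Both:* s = .5 with 3 extra sessions gives .811, power .901; s = .9 with 6 extra gives .968, power .944.
- *Serial correlation:* with assumed smooth hormone curves, AR(1) residuals of .3 to .7, 25% missed and daily power set to .95, power is about .83 to .93 on the exact reading and .84 to .95 on the floor reading.

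**The case against.** The strongest reply is that no failed calculation has been shown. If daily is only leftover wording, the .95 stands and one word needs changing. That is fair, and the point made here is only that the figure is unsupported as written.

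Second, .70 to .72 is a pessimistic illustration. It assumes independent days, no slope variance, no extra sessions and .95 exact at 27 days. The plan's wording can be read as a floor, and serial correlation with slowly changing hormones makes alternate days nearly as informative as daily ones. This stands. The loss may be modest, and the most favourable serial-correlation setting practically recovers .95.

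Third, the Aim 1 draw count is 14 to 20 per cycle, above the 13.5 used here. With 14, 17 or 20 sessions and 25% missed, power is .82, .89 or .93 on the floor reading and .74, .82 or .87 on the exact reading. The count is the plan's own, but 20 alternate-day sessions imply a 40-day cycle, outside the 22 to 32 days of the power statement. They give 60 × 20 × .75 = 900 sessions, and reaching 990 takes 4 more per non-user (30 × 4 × .75 = 90). The count also supports the alternate-day reading, since daily draws over two cycles of 22 to 32 days would number 44 to 64.

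Fourth, favourable inputs could still give .95 on alternate days over 27 days: three independent muscles with no missed visits, or four with 25% missed, each give .959. In both cases the matching daily power would be about .999 rather than the .95 stated.

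Finally, the study tests no intervention (section 4.b), so no treatment decision rests on this figure. That is true, but the figure still carries the inference for two of the four aims.

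**Conclusion.** The concern holds. The .95 is tied in writing to daily sessions, the operative schedule is every other day, and neither the cycle-length range nor the 25% allowance covers halving the sessions. This conclusion rests on the text and session counts alone.

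The size of the loss is not known. Under independent days and two-sided 5%, power at -0.075 would be about .70 to .72 on the exact reading (r of .106 to .109 detectable at .95), or .79 to .81 on the floor reading (r of .096 to .098). Extra sessions, slope variance or serial correlation would reduce the loss, in the best cases to almost nothing. All these figures are illustrations, because the simulation's alpha, residual correlation and slope variance are not stated.

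**What to change.** Reconcile the frequency of testing and blood draws across Procedures Involved, the Figure 1 legend, the Aim 1 venipuncture paragraph, the sample size section and the 4.d table.

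If the simulation already used every-other-day sessions, say so and correct the word daily. If it did not, rerun it on the schedule in use, including any additional reflex sessions on TMS days, with the same cycle lengths and 25% missed visits. In either case, state the alpha and sidedness, the residual correlation (between muscles and between days) and the between-woman slope variance. Then give the power at -0.075, or the correlation detectable at .95.

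The cost is at most one rerun of an existing simulation and a few sentences, with no added participants or visits. The restated power will probably be less favourable, and the rule-out claim should then be worded to match it.

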The goal of this project is to test our central hypothesis that changes in sex hormone concentration result in changes to the basic elements of motor control – at multiple levels, from the musculotendinous unit to motor control circuitry. Under Aim 1 we will determine the influence of sex hormone fluctuations on the muscle stretch reflex during active and passive states, and the time lag between hormone concentration changes and the reflex response. We will use a technically simple assessment that could be implemented in the field. Under Aim 2 we will determine the influence of sex hormone fluctuations on spinal motor neuron excitability using H-reflex as a probe and the simultaneous change in the muscle mechanics using muscle twitch response. Aims 1 & 2 will include a focus on the differential role of oral contraceptives. In Aim 3 we will use paired-pulse transcranial magnetic stimulation during active contraction to determine the influence of sex hormone fluctuations on cortical excitability in naturally cycling women. In the basic elements of motor control explained in Aim 2 and Aim 3 is that the sex hormones modulate the synaptic transmission and plasticity of neuron and muscles. The modulation of the synaptic transmission and plasticity of neuron and muscles might be caused by the changes of the neurotransmitter or muscle fiber in the transcriptional level, translational level, or combination of both. In Aim 4, we want to explore these changes through sequencing of whole exome and microRNA in addition to evaluating the expression level of mRNA and proteins related to synaptic transmission and muscle. Our findings have the potential to guide future research in injury prevention strategies, including targeted neuromuscular training. This knowledge will enable clinicians to educate female patients on neuromuscular effects of sex hormones during times of high fluctuations, including puberty, pregnancy, and menopause.

Abbreviations:

nOC = non- users of oral contraceptives

OC = oral contraceptive users

2. Background.

- Describe past experimental and/or clinical findings leading to the formulation of your study.
- For research involving investigational drugs, describe the previously conducted animal and human studies.
- For research that involves FDA approved drugs or devices, describe the FDA approved uses of this drug/device in relation to your protocol.

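### The single power of .95 for Aims 1 and 2 is not shown to hold for the Aim 2 H-reflex alone; with one value per visit, daily visits and 25% missed, it is about .63 to .80 (two-sided 5% assumed)

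*Combined protocol and SAP*

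**What the plan says.** The purpose statement at the start of the protocol separates the two questions. Aim 1 concerns the muscle stretch reflex. For the other, "Under Aim 2 we will determine the influence of sex hormone fluctuations on spinal motor neuron excitability using H-reflex as a probe". The Aim 1 and Aim 2 procedures in 4.a use different muscles, positions and stimuli.

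The Sample Size Justification in 4.a treats the two aims together. Its stated purpose is to exclude a hormonal effect on motor neuron excitability. The inputs it gives are:

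- Subjects: "Pooling $N = 30$ OCs and $N = 30$ nOCs".
- Outcomes and power: "daily H-reflexes from soleus muscle (Aim 1) and MSR from 3 quadriceps muscles (VM, VL, RF) over one menstrual cycle provided power = .95".
- Effect: an "average within-individual correlation of $r = -0.075$ ($R^2 = .005$) between a single hormone and reflex responses".
- Robustness: "This degree of power holds even if menstrual cycles vary from 22 to 32 days", and also if "participants miss an average of 25% (see above) of their lab visits".

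It does not give alpha, sidedness, the correlation among the reflex series, or whether the unit of analysis is a visit mean or a single trial. It gives no separate figure for the H-reflex.

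**The concern.** One figure covers two aims, and the outcomes behind it are unequal in number: three muscles bear on Aim 1 and one on Aim 2. A power that depends on all four series need not apply to the one that answers Aim 2. The H-reflex label compounds this, because a reader of the power paragraph alone would not see that Aim 2 rests on the single soleus series.

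The figure matters most if the result is null. The paragraph's purpose is to exclude an effect on motor neuron excitability, which is the construct that defines Aim 2. With .95 power, a null H-reflex result would be read as carrying a 5% risk of missing r = .075. If the real power is much lower, that reading is wrong for the outcome where it counts most.

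**Working it through.** **Inputs from the plan.** 60 women; one cycle of 22 to 32 days (midpoint 27); daily visits in the power text; 25% missed; |r| = .075; four reflex series.

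**Assumptions.** Alpha 5%, two-sided, with one-sided as a variant. One H-reflex value per visit (the mean of that visit's replicates). Independent residuals and the same slope in every woman. Serial correlation or slopes that differ between women would usually lower power.

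**Formulas.** Removing each woman's mean leaves df = 60 × days × 0.75 − 60. Power = Φ(r√df / √(1 − r²) − z), with z = 1.960 two-sided or 1.645 one-sided.

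**What .95 requires.** Two-sided: df = ((1.960 + 1.645)/.075)² × (1 − .075²) ≈ 2,297. One-sided: about 1,913.

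**One H-reflex value per visit, daily visits, 25% missed:**

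| Cycle (days) | df | Two-sided 5% | One-sided 5% |
|---|---|---|---|
| 22 | 930 | .63 | .74 |
| 27 | 1,155 | .72 | .82 |
| 32 | 1,380 | .80 | .88 |

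For 27 days: .075 × √1,155 / √(1 − .075²) = 2.556; 2.556 − 1.960 = 0.596; Φ = .72. A simulation with person-centred regression gave .64 at 22 days, .71 for mixed 22 to 32 day cycles, and .81 at 32 days.

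**No missed visits.** Two-sided .76, .84, .90; one-sided .85, .91, .945.

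**Every other day, 25% missed, two-sided.** Visits are halved, so df = 435, 547.5 and 660, and power is .35, .42 and .49.

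**Detectable r at .95.** For 27 days, daily, 25% missed, two-sided: 3.605/√1,155 = .106, or .105 with the √(1 − r²) term.

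**Reproducing the plan's .95.** It cannot be confirmed from the stated inputs alone. Two unstated routes reach it at two-sided 5% with 25% missed:

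1. *Pooling the four series.* df is multiplied by 4/(1 + 3ρ), where ρ is the correlation among series. At 27 days the multiplier needed is 2,297/1,155 = 1.99, so ρ = (4/1.99 − 1)/3 ≈ .34 or less. At 22 and 32 days the limits are about .21 and .47. Simulation with ρ = 1/3 and cycles of 22 to 32 days gave .956.
2. *Counting replicates.* The Aim 2 procedures take five measurements at the peak H-reflex per session. If r refers to single trials, df is multiplied by 5/(1 + 4ρ), where ρ is the correlation among replicates. At 27 days ρ = (5/1.99 − 1)/4 ≈ .38 or less; at 22 and 32 days, about .26 and .50.

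**Aim 1 for comparison.** Averaging three quadriceps series at 27 days, daily, 25% missed, two-sided, gives .88 if their correlation is .5 and .96 if it is .2. The Aim 1 figure also depends on an undisclosed correlation.

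**The case against.** Several points on the other side have force.

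- *Pooling across muscles is inferred.* In the plan the word for pooling governs the two cohorts, not the reflex series. A reader might infer that the four series were demonstrably analysed as one and that .95 is a miscalculation. The documents do not support that: the simulation's settings are undisclosed, so the figure is unverifiable rather than shown to be wrong.
- *The H-reflex is measured more than once per session.* A reader might infer that Aim 2 yields one value per visit and that .95 could come only from pooling muscles. The five replicates are a second route. It needs a trial-level analysis and fairly weak correlation between responses seconds apart, neither of which is stated.
- *Alpha and sidedness are assumed.* The effect is written with a sign, so a one-sided test is possible. A miss risk of 20% to 37% is therefore not a fact of the plan; at one-sided 5% it is about 12% to 26%. Both ranges include the plan's 25% missed visits.
- *Separate conclusions for the two aims are not spelled out.* A joint model for both reflexes could make one joint figure coherent.

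The last point does not remove the gap. The purpose statement makes these distinct aims, and the Aim 3 paragraph shows the missing step: it gives a pooled GEE power and then a separate .80 for each inter-pulse interval at a stated alpha. Nor does sidedness rescue the figure. No visit-level, single-series variant with 25% missed reaches .95; the highest is .875 (one-sided, 32 days).

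**Conclusion.** The point holds in conditional form. The documents do not show .95 power for the H-reflex alone. With one averaged value per visit and the power text's own visit frequency and missingness, power is about .63 to .80 at an assumed two-sided 5%, or .74 to .88 at one-sided 5%. On the every-other-day schedule in Procedures Involved and table 4.d it is about .35 to .49 (two-sided), so reconciling the visit schedule alone would not cure the shortfall.

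The plan may have reached .95 by pooling series or by counting replicates. Either rests on a correlation and an analysis unit that it does not disclose. The H-reflex label in the power paragraph contradicts the statement of purpose whatever the power turns out to be.

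**What to change.** 1. Rerun the existing simulation separately for Aim 1 (stretch reflex) and Aim 2 (H-reflex), after reconciling the daily visits of the power text with the every-other-day testing in the procedures.
2. State alpha, sidedness, the analysis unit (visit mean or single trial), and the assumed correlations among muscles and among replicates.
3. Replace the single .95 with one power figure per aim, or the r detectable at .95 power per aim. The approximations above should not be pasted in; the rerun should supply the figures.
4. Relabel the H-reflex as Aim 2.
5. Do not describe a null H-reflex result as excluding r = .075 on the strength of the joint .95.

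The cost is one rerun and some rewording, and probably a less favourable power figure for Aim 2.

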subject control. Based on preliminary data of four subjects, at each of the 6 ISIs >7 ms (see Fig. 6), a sample size of 20 subjects achieved over 90% power to detect a main effect for a GEE model that pools the ISIs as correlated outcomes. Additionally, we have sufficient power (.80) to follow up a main effect, for each of the six ISIs, to detect differences of 40% or larger from the null hypothesis, with an estimated standard deviation of 37% and with a significance level (alpha) of a Bonferroni-corrected $0.05/6 = 0.008$. To allow for attrition we will aim to enroll 30 subjects in each female cohort. To ensure that our within-subject changes can be attributable to changes in the hormonal milieu, we will enroll $N = 15$ males and test them at multiple occasions.

4.b. List of the study intervention(s) being tested or evaluated under this protocol

 N/A - this study does not test or evaluate an intervention. Skip to item 4.d.			
#	Study intervention(s) being tested or evaluated under the protocol Add or delete rows as needed	Affiliate Place a check next to institution(s) where the intervention will be performed	Local Standard Practice? Indicate whether the intervention is considered acceptable practice locally for applicable institutions
1	Insert study intervention 1 here	 UTSW  PHHS  CMC  THR  TSRH  Other: _____	 Yes  Yes  Yes  Yes  Yes  Yes
2	Insert study intervention 2 here	 UTSW  PHHS  CMC  THR  TSRH  Other: _____	 Yes  Yes  Yes  Yes  Yes  Yes

4.c. Risk:Benefit Analysis of study interventions being tested or evaluated under this protocol

For each study intervention identified in section 6b above, complete a risk:benefit analysis table.

(Two tables are provided, copy & paste additional tables as needed or delete both tables if this study does not test an intervention)

Form A

IRB Velos	STU-2018-0192 26783

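### Aim 3 tests hypothesis 3 with a pooled GEE on 20 to 30 women and names no small-sample inference; the ordinary GEE test would run at 6.4–7.1%, not 5%

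*Combined protocol and SAP*

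**What the plan says.** The only account of the Aim 3 analysis is the Aim 3 paragraph of the Sample Size Justification in section 4.a of the combined protocol and SAP.

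- **Hypothesis.** It is directional: "that estradiol will produce a targeted facilitatory influence on lower limb muscles".
- **Model.** "we used a GEE model that views the mean conditioned MEPs at each ISI as correlated outcomes before separate post-hoc tests". The post-hoc tests are made at each of six inter-pulse intervals (ISIs), and peak estradiol is compared with baseline within subject.
- **Size.** "a sample size of 20 subjects achieved over 90% power to detect a main effect for a GEE model that pools the ISIs". Then: "To allow for attrition we will aim to enroll 30 subjects in each female cohort". The summary of aims restricts Aim 3 to naturally cycling women, which is one cohort, so the GEE has 20 to 30 independent women.
- **Follow-ups.** Power of .80 is claimed for differences of 40% or more, "with an estimated standard deviation of 37% and with a significance level (alpha) of a Bonferroni-corrected" 0.05/6.
- **Males.** Under Procedures Involved, "The control group for all Aims will be age-matched healthy males". The sample size text adds: "we will enroll $N = 15$ males and test them at multiple occasions", so that within-subject changes can be attributed to hormones.

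For the main effect the paragraph names no variance estimator, reference distribution, degrees of freedom or small-sample correction.

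**The concern.** A GEE sandwich variance is justified when the number of independent subjects is large. With 20 to 30 it is biased downwards, and a normal reference ignores that it was estimated from few subjects. Both errors push towards rejection. Six ISIs per woman add rows but no independent subjects.

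The main effect is the first test of hypothesis 3 and opens the ISI tests. If it rejects too often, a claim that cortical excitability changes with estradiol, resting on the pooled effect alone, carries more false-positive risk than its nominal level. Analysing all 30 enrolled women reduces the excess but does not remove it.

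**Working it through.** **Inputs from the documents:** n = 20 (power statement) and 30 (enrolment); six ISIs; follow-up difference 40%, SD 37%, alpha 0.05/6.

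**Assumptions not in the documents:** main effect tested two-sided at 0.05, 1-df contrast of peak estradiol with baseline, women only, normal within-woman changes, complete data.

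**Step 1: the plan's own figures.** 0.05/6 = 0.0083, which rounds to the stated 0.008. The follow-up power of .80 is approached by a two-sample z formula: 40/(37·√(2/20)) = 3.419, less 2.638, gives 0.78. The main-effect figure of over 90% cannot be reproduced, because the pooled effect and the between-ISI correlation ρ are not given in the text. Borrowing 40% and 37%, the SD of the six-ISI average is 37·√((1+5ρ)/6). In the worst case, ρ = 1, a paired t with 20 women has power of 99.6% if 37% is the SD of the change. If 37% is the SD per occasion, with no correlation between occasions (change SD 37·√2 = 52.3), power is 90.0%. The stated figure is not contradicted.

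**Step 2: Type I error of the ordinary test.** Let d be a woman's change averaged over ISIs. In balanced data the uncorrected sandwich SE is √(Σ(d − mean)²)/n, while the paired-t SE is √(Σ(d − mean)²/(n(n − 1))). Hence Wald = t·√(n/(n − 1)), and |Wald| > 1.960 is the same event as |t| > 1.960·√((n − 1)/n) on n − 1 df.

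| Women | Effective cut-off for t | Correct cut-off | Type I error |
|---|---|---|---|
| 20 | 1.910 | 2.093 | 7.13% |
| 25 | 1.920 | 2.064 | 6.68% |
| 30 | 1.927 | 2.045 | 6.38% |

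Simulation with 200,000 data sets gave 7.09% (20) and 6.35% (30). Half of these errors lie in the direction of facilitation: 3.57% and 3.19%, against 2.5%.

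**Step 3: other versions that the text leaves open.** For the joint 6-df tests, the Wald statistic rejects when F(6, n − 6) > 12.592·(n − 6)/(6n), and the score statistic when F(6, n − 6) > 12.592·(n − 6)/(6(n − 12.592)).

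| Test | n = 20 | n = 30 |
|---|---|---|
| 1 df, uncorrected sandwich, normal | 7.13% | 6.38% |
| 1 df, SE with n − 1, normal | 6.48% | 5.97% |
| 1 df, uncorrected sandwich, t(n − 1) | 5.55% | 5.37% |
| 1 df, score test | 4.69% | 4.81% |
| 1 df, paired t | 5.00% | 5.00% |
| Joint 6 df, Wald chi-square | 25.83% | 16.95% |
| Joint 6 df, score chi-square | 1.58% | 2.88% |

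A model-based exchangeable SE gave 4.8% in simulation when its structure was right. It gave about 19% to 36% when women differed in their occasion shift (assumed SD 0.5 to 1.0 of the residual SD).

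**Step 4: sensitivity of the 1-df Wald-z figure.** With 25% of visits missing at random (borrowed from the Aims 1 and 2 text), simulation gave 6.5–7.8% (20 women) and 6.0–6.7% (30). Skewed changes (assumed lognormal, log-SD 0.36) gave 8.2% and 7.3%. So 6.4–7.1% is not an upper bound.

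**Step 5: follow-ups.** A Wald-z follow-up at nominal 0.83% runs at 1.9% (20) or 1.5% (30). With t-based follow-ups behind an uncorrected gate, the simulated chance of any false ISI claim was 1.1–2.8%.

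**Step 6: power cost of a valid test.** The noncentrality that gives exactly 90% at the uncorrected cut-off is 3.227 (20 women) or 3.232 (30). At the correct t cut-off the same noncentrality gives 86.4% or 87.8%.

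**The case against.** The strongest reply is that no error has been shown. The documents never name a Wald-z test, and the inflated figure needs an uncorrected sandwich, a normal reference, 1 df and a two-sided 0.05, none of which is stated. The GEE sentence is in the past tense, in a sample size section of an ethics-board form. This stands: the excess is conditional. It does not dispose of the point, because the uncorrected sandwich with a normal reference is how a plain GEE is normally run, and no other Aim 3 analysis text overrides it.

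The effect is also small. At n = 20 the ordinary test and a paired t disagree only when |t| lies between 1.91 and 2.09, and ISI-specific claims have their own Bonferroni level. This stands too and sets the priority.

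Three stronger readings are tempting, and the documents support none of them:

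- **That Aim 3 has an inflated error rate.** The test is unnamed, and some open versions are at or below 5%.
- **That any version other than Wald-z is safe.** The second table shows otherwise.
- **That the over-90% power claim is wrong.** Step 1 does not contradict it. The drop to 86–88% applies only if power under the uncorrected test were exactly 90%, and the plan claims more than that.

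The main-effect alpha and sidedness, and whether males and the other TMS visits enter the model, are missing detail and not evidence of error. The within-subject contrast and the stated reason for enrolling males partly answer the last of these.

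**Conclusion.** The point holds in conditional form. Hypothesis 3 rests first on a pooled GEE main effect in 20 to 30 women with no small-sample inference named. Run in the ordinary way on 1 df, it rejects a true null 7.1% of the time with 20 women and 6.4% with 30, an excess of 1.4 to 2.1 points. That rests on a two-sided 5% level, normal changes, complete data and women only. The sandwich-based versions in the second table run from about 2% to 26%, so what is established is a risk of the default method. Low priority: in the 1-df case it is a small excess on one pooled claim in one aim, and it can be avoided at little cost.

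**What to change.** In the Aim 3 analysis text:

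1. Define the main effect as a 1-df contrast of peak estradiol with baseline, pooled over ISIs, at two-sided 0.05.
2. Name a small-sample-valid test. Examples are a paired t on each woman's ISI-averaged change, or a bias-corrected sandwich (such as Kauermann-Carroll) with t on n − 1 subject-level degrees of freedom. The two are equivalent in balanced data.
3. Make the six follow-ups t-based at 0.05/6.
4. Recheck the over-90% power with that test, and report the pooled effect, SD and between-ISI correlation used.

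The same sentences can say whether males and the other TMS visits enter the model. If males are part of the contrast, a Welch t on subject-level changes is well calibrated (5.0% in simulation with 15 males and equal SDs).

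The cost is two or three sentences and a standard software option, with no extra subjects or visits. The downside is about 2–4 points of power if the uncorrected test had exactly 90%.
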